****The 2 least accurate of the 3 individual phrase probes will be selected as therapy targets.**

Progress monitoring Assessment (~40 minutes): Conducted after 5 weeks, 10 weeks, and 15 weeks.

1. Multisyllabic Word Repetition Task ([name] & Edwards, 2007). ~10 minutes. Participants will repeat multisyllabic words of 2-5 syllables after the word is presented via computer. Percent consonants correct, percent lexical stress correct, and number of syllable segregations will be obtained.
2. Multisyllabic Picture Naming. ~5 minutes. Participants will name 30 researcher-selected multisyllabic words presented via pictures on PowerPoint slides. Percent consonants correct, percent lexical stress correct, and number of syllable segregations will be obtained.
3. Word Inconsistency subtest of Linguisystems Articulation Test (Bowers & Huisinigh, 2011). ~5 minutes. Participants will name 12 multisyllabic pictures 3 times each following an initial model (e.g., "Say *eyelashes* three times). Productions will be evaluated on whether the 3 trials are consistent (C) or inconsistent (I). Additionally. Percent consonants correct, percent lexical stress correct, and number of syllable segregations will be obtained from the first production of each set.
4. Phrase repetition task. ~10 minutes. Participants will repeat phrases and short sentences containing multisyllabic words after the phrase/sentence is presented via computer (e.g., "factual discussion;" "Renew my newspaper subscription."). Percent consonants correct, percent lexical stress correct, and number of syllable segregations will be obtained.
5. Three Individual Phrase Probe Lists. ~5 minutes each, 15 minutes total. Based on speech sound errors observed in Baseline 1, specific error patterns will be identified. Individual probes addressing an error pattern will be administered. Participants will read a list of 20 phrases containing the target pattern (e.g., for onset /l/ examples might be: "please go left" and "light the flame"). Percent accuracy will be collected on number of target sounds produced correctly out of 40 using a binary scoring system (i.e., incorrect = 0; correct = 1).
6. Ultrasound Safety Form (for those receiving US biofeedback). ~5 minutes. Administer a short questionnaire to participant and parent to ensure that procedures and methods continue to be safe and are without adverse effect.

Treatment Design

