Aim 1: In addition to the above assessment visits, participants will be randomized to one of four treatment conditions.

Table 1: Four groups to which children will be randomized in a 2 x 2 Factorial design

Distribution Conditions	Biofeedback Conditions	
	Sequenced Biofeedback (Biofeedback → No biofeedback)	No biofeedback
Sequenced Distribution (massed→distributed)	n=10	n=10
Distributed Practice	n=10	n=10

We will randomize children with CAS to one of four groups. We will test generalization effects in a x 2 (Mass→Distributed vs. Distributed only Practice Schedule) x 2 (Sequenced Biofeedback→No biofeedback vs. No biofeedback) factorial treatment design.

Participants will be randomly assigned to either Distributed Practice or Sequenced Distribution (massed→distributed practice). In both conditions, the cumulative treatment dose will be 20 hours of treatment. Half of our participants (n=20) will receive treatment following a distributed model of twice per week for 60 minutes for 10 weeks, for a total of 20 hrs of therapy. The remaining participants (n=20) will receive treatment following a sequenced approach of massed then distributed practice, with 10 hrs occurring in the first week (2 hrs per day for 5 days, with a 10 minute break in between sessions each day), then 3 one-hour sessions per week for 2 weeks, and finally 2 one-hour sessions per week for 2 weeks.

Table 2: Overview of Aim 1 Schedule by Group: Operationalized Definitions

	Wk 1	Wk 2	Wk 3	Wk 4	Wk 5	Wk 6	Wk 7	Wk 8	Wk 9	Wk 10	Wk 15
Distributed Practice Group (n=20)	1 hr x 2 visits & Assess	1 hr x 2 visits & Assess	Assess								
Sequenced Distribution Group (n=20)	2 hr x 5 visits	1 hr x 3 visits	1 hr x 3 visits	1 hr x 2 visits	1 hr x 2 visits & Assess	-	-	-	-	Assess	Assess

Aim 2: In addition to the above randomization based on schedule, half of the participants (n=20) will be randomized to receive treatment without ultrasound visual feedback and half (n=20) will be randomized to receive treated with ultrasound. The practice structure described above (see *Overview of Treatment Procedures*) will be identical, and the difference between conditions therefore will be whether or not the clinician and client have access to a visual referent during speech production to describe aspects of both erred and correct tongue movements.

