A manual has been developed outlining the protocols that are to be followed. All members of the team will be required to read the manual to ensure familiarity with technical and procedural issues. We will hold weekly lab meetings to review both procedural/compliance issues as well as scientific issues. We will outline responsibilities at each meeting (currently using the web-based system ASANA) and we will keep a running log of the status of recruitment, participation, data collection, data safety/confidentiality, and data analysis. All members are CITI-certified and will be instructed to immediately bring to the PI's attention any Human Subjects related issues.

6.5. Explain how you will have adequate numbers of qualified staff to conduct your study.

The staff listed above are sufficient to collect and manage data from approximately 15 children per year and to conduct data management/coding activities for those participants.

7. Characteristics of Participants

7.1. Approximate Number of Participants to be recruited: 40

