7.2. Sex: M F Both

7.3. Age Range-Check all that apply:

0-6 (Include parental consent form)
 7-17 (Include parental consent form and child assent form)
 18-64
 65 and older

Exact ages to be included: 9;0 – 17;11

7.4. When the age range indicates an upper limit, provide justification: This age range is chosen as it is sufficiently restrictive to enable homogeneity of participants, with all participants beyond the age of typical acquisition of speech sounds (approximately age 8-9 yrs, Smit et al., 1990); additionally, prior work has shown that children below the age of 8 may show less growth with biofeedback treatments (Sjolie et al., 2016). Because participants may be randomized to a treatment condition with an intensive component (e.g., 10 hours of therapy over 5 consecutive days), participants need to be old enough to maintain attention to cognitively demanding tasks over long durations.

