Risks associated with the speech production and assessment components of this study are no greater than those in daily life. The ultrasound portion of this study likewise involves no more than minimal risk. Diagnostic ultrasound imaging is regarded as a safe and non-invasive technology (see Epstein, 2005, for a summary of this research). While a number of epidemiological studies have investigated the effects of ultrasound on various types of tissue, no negative effects have been documented as a consequence of exposure to diagnostic ultrasound of the type used in this study (Ziskin & Petitti, 1988; Barnett et al., 2000). Although certain types of ultrasound carry a slight risk that the temperature of the ultrasound probe may increase by 1-4 degrees Celsius during imaging, these thermal effects have never been associated with the type of imaging used in this study. Studies have demonstrated that the imaging mode used in this study (B-mode) is rarely associated with probe temperature increases of even one degree Celsius. Other risks associated with use of the ultrasound include transfer of communicable disease from one person to another (such as the common cold) if the ultrasound probe is not disinfected between participants.

Risks associated with the treatment portion of the study are those which would be associated with any speech-language therapy in schools. This includes frustration and/or boredom during completion of tasks.

12.2. Describe what procedures will be used to minimize each risk you have stated above. Also, include in your description the availability of medical or psychological resources that participants might require as a consequence of the research, if applicable. If participants need to be debriefed at the end of the study, a copy of the debriefing statement must be attached.

- To keep ultrasound exposure to an appropriately limited amount, we only expose the participant to ultrasound for approximately 13 minutes at a time, for less than half the session.
- To ensure that the risk of communicable diseases is reduced, we clean the ultrasound with approved products between users (before and after each session).

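### The only safety questionnaire described goes to the ultrasound arms alone, so adverse effects are actively asked about in 20 of 40 children, with no comparator for ultrasound

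*Protocol*

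**What the plan says.** The protocol describes one safety questionnaire. It is item 6 of the progress assessment in section 4.1: "Ultrasound Safety Form (for those receiving US biofeedback). ~5 minutes. Administer a short questionnaire to participant and parent". Its stated purpose is wider than its title: "to ensure that procedures and methods continue to be safe and are without adverse effect". The timing is that of the assessment itself: "Progress monitoring Assessment (~40 minutes): Conducted after 5 weeks, 10 weeks, and 15 weeks". Items 1 to 5 of the same visit are speech measures and go to every child.

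Section 12.1 separates two kinds of risk. One belongs to the ultrasound probe (heating, infection). The other belongs to the therapy: "This includes frustration and/or boredom during completion of tasks". The therapy is common to all four groups.

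Elsewhere, section 12.2 answers boredom and frustration with scheduled breaks. Section 6 tells staff to take human-subjects issues to the principal investigator at once. The SAP contains no safety or tolerability analysis.

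**The concern.** When one side of a randomised comparison is asked about adverse effects and the other is not, the reports cannot be compared. A solicited complaint from an ultrasound child may come from the probe, from the therapy or from neither, and the answers that would help to tell these apart are not collected. Yet the controls attend the same visits at the same weeks.

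The gap also touches the other randomised factor. Half of the children on the massed schedule, those without ultrasound, are never asked. Any statement about how children tolerated that schedule would rest on the ultrasound half.

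What is at stake is the description of harms. The efficacy estimate is not affected.

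**Working it through.** **Inputs.** Section 7.1 gives "Approximate Number of Participants to be recruited: 40". Table 1 in section 4.1 gives four cells of 10. Item 6 gives the restriction and the 5 minutes. Table 2 gives the visits. The documents give no complaint rate, no dropout rate and no power calculation, so any rate below is an assumption.

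**The plan's own counts.** 4 × 10 = 40 in total; 2 × 10 = 20 with ultrasound; 2 × 10 = 20 without. These reproduce.

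**Who is asked, as planned.**

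| Cell | n | Given the form |
|---|---|---|
| Massed then distributed, ultrasound | 10 | 10 |
| Massed then distributed, no ultrasound | 10 | 0 |
| Distributed, ultrasound | 10 | 10 |
| Distributed, no ultrasound | 10 | 0 |

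- Coverage: 20/40 = 50%.
- Forms: 20 × 3 = 60 in the ultrasound arms and 0 in the others.
- Ultrasound contrast: 20 respondents against 0.
- Schedule contrast: 10 against 10, inside the ultrasound arms only.

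**What wider coverage buys.** If no child reports anything, the one-sided 95% upper bound on the complaint rate is 1 − 0.05^(1/n):

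- n = 10 (one cell): 25.9%
- n = 20 (as planned): 13.9%
- n = 40 (all children): 7.2%

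**What it does not buy.** Power for 20 against 20 at two-sided 0.05, under assumed rates:

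- 10% v 30%: 0.35 (normal approximation), 0.24 (Fisher)
- 10% v 50%: 0.81 (normal approximation), 0.74 (Fisher)

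For the surviving 10 against 10 schedule contrast, Fisher power at 10% v 50% is 0.295.

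**Illustration only.** Suppose that the form asks general questions and that 10% to 30% of children would voice some complaint about any such therapy. Then 20 × 0.10 = 2 to 20 × 0.30 = 6 ultrasound children would report one even if ultrasound were harmless. The chance of at least one report is 1 − 0.9^20 = 0.878 to 1 − 0.7^20 = 0.999.

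**Timing.** In the massed ultrasound cell, cumulative hours are 10, 13 and 16 at the ends of weeks 1, 2 and 3, and ultrasound stops for the last 4 of 20 hours. The week 5 form therefore comes about 2 weeks after the last ultrasound use and about 4 weeks after the massed week. In the distributed cell, hour 16 falls in week 8 (8 × 2 = 16).

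**Visit length.** The listed speech items take 10 + 5 + 5 + 10 + 15 = 45 minutes. With the form the total is 50, against about 40 stated.

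**The case against.** The best defence is that this is a device check. It is named for the ultrasound, and only two arms are planned to receive ultrasound as treatment. The trial poses no harms question, and section 12.3 asks for a monitoring plan only above minimal risk. Boredom and frustration are handled in every arm by breaks, staff escalation, parental observation and the right to withdraw. This stands as a reason to rate the point low. It does not remove the asymmetry: the form's stated purpose is general, breaks are mitigation and not measurement, and staff escalation depends on someone raising a problem unasked.

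It is also fair that the form's items cannot be seen, since section 4.3 sends instruments to appendices that are not in the supplied text. If every item concerns the probe, most would make no sense for controls, and the illustration above falls away.

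A reader might infer more than the documents support:

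- **That the form unmasks outcome assessment.** Section 3.1 claims blinding for the scorers, section 11.2 has outside listeners hear single words in random order, and the form is listed after all the speech tasks. No text has raters hearing it.
- **That the benefit-risk statement in section 13.3 rests on these reports.** It is a judgement made in advance for the ethics board.
- **That section 7.4 raises the intensive week as a safety concern.** Its remark that "participants need to be old enough to maintain attention to cognitively demanding tasks over long durations" justifies the age range.
- **That schedules cannot be compared at all.** The 10 against 10 contrast survives.
- **That frustration is measured in the ultrasound half.** Nothing shows this.

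**Conclusion.** The point holds as a minor one, to be considered. The only safety questionnaire in the text solicits adverse effects in 20 of 40 children and in 0 of the 10 in the massed no-ultrasound cell. It has no concurrent comparator for ultrasound and supports a schedule comparison only within the ultrasound arms. This follows from Table 1 and item 6 and needs no assumed rate.

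It rests on two readings: that no further safety form lies in the missing appendices, and that the form's content matches its general purpose. No stated aim or efficacy conclusion depends on it. The gain from a change is descriptive: full coverage, and a zero-event bound of 7.2% in place of 13.9%. It would not give a test able to separate an ultrasound effect from ordinary fatigue.

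A related inconsistency bears on who is exposed. Section 11.1 makes collection of ultrasound images depend on the randomised condition, while section 11.7.2 requires every participant to agree to ultrasound video. The second may be only consent in advance of allocation, but the text does not say so. If children in the no-biofeedback arms are imaged, they are exposed without the form.

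**What to change.** In item 6, replace the restriction with all participants. Put a short common set of general questions (discomfort, fatigue, frustration, any adverse effect) to all 40 children and their parents at the week 5, 10 and 15 visits, after the speech tasks. Add probe-specific questions only for children exposed to ultrasound. Keep both parts within those visits: in Table 2 the massed groups have no treatment session after week 5, and no group has one at week 15. Tabulate the answers by the four randomised groups, with no significance test, and add one sentence to the SAP saying so. Reconcile sections 11.1 and 11.7.2 so that it is clear which children are exposed to ultrasound.

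**Cost.** One form revision, one descriptive table, and 20 × 3 × 5 = 300 minutes (5 hours) of visit time in total, with no new visit. The drawbacks are real. The listed items already exceed the stated visit length, the week 5 questions come about four weeks after the massed week, and the comparison has low power.

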In the Sequenced Biofeedback → No biofeedback condition, participants begin treatment such that ~50% of the session includes ultrasound feedback of the tongue. Each session will be divided into four 13 minute Time Periods (A, B, C, D). The ultrasound will be available for practice in Time Periods A and C, whereas practice will continue without ultrasound for periods B and D. When the ultrasound is used in Time Periods A and C, it will be available only when the participant is practicing at treatment Levels 1 (syllables), 2 (monosyllabic words), 3 (multisyllabic words) and 4 (phrases). However, after 8 hrs of treatment, *ultrasound use will be faded* such that it is only available as children are at practice Levels 1 and 2 to encourage independent practice without visual support at more complex levels. During the final 4 hours of treatment, no visual feedback will be available.

[figure not shown]
Table 3: Structure for a 60-min Session: Operationalized Comparison of Ultrasound use for Aim 2

Sequenced Biofeedback → No Biofeedback Group (n=20)				
Time Period:	A	B	C	D
Treatment target	Target 1	Target 1	Target 2	Target 2
Ultrasound available: First 8 hrs of therapy	Used on Levels 1: Syllables 2: Monosyllabic words 3: Multisyllabic words 4: Phrases	None	Used on Levels 1: Syllables 2: Monosyllabic words 3: Multisyllabic words 4: Phrases	None
Next 8 hrs of therapy	Used on Levels 1: Syllables 2: Monosyllabic words	None	Used on Levels 1: Syllables, 2: Monosyllabic words	None
Last 4 hrs of therapy	None	None	None	None
No Biofeedback Group (n=20)				
Time Period:	A	B	C	D
Treatment target	Target 1	Target 1	Target 2	Target 2
Ultrasound use	None	None	None	None

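### In the Sequenced Distribution ultrasound cell (planned n=10), no Ultrasound Safety Form is given while ultrasound is in use: ultrasound ends with week 3 and the first form comes at week 5

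*Protocol*

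**What the plan says.** **The form.** In Protocol section 4.1, the Ultrasound Safety Form is item 6 of the progress monitoring assessment: "Ultrasound Safety Form (for those receiving US biofeedback). ~5 minutes". Its purpose is to "Administer a short questionnaire to participant and parent to ensure that procedures and methods continue to be safe and are without adverse effect". The timing belongs to the assessment as a whole: "Progress monitoring Assessment (~40 minutes): Conducted after 5 weeks, 10 weeks, and 15 weeks". The form is not listed among the Baseline 1 or Baseline 2 tasks or in the treatment session procedures.

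**The schedules.** Under Treatment Design, Aim 1, both schedules deliver 20 hours. The Sequenced Distribution schedule begins "with 10 hrs occurring in the first week (2 hrs per day for 5 days" and continues "then 3 one-hour sessions per week for 2 weeks, and finally 2 one-hour sessions per week for 2 weeks". The Distributed Practice schedule is two one-hour sessions a week for 10 weeks. Table 2 places the Sequenced group's assessments in weeks 5, 10 and 15 only.

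**Ultrasound availability.** Under Aim 2 and its session-structure table, ultrasound can be used in two of the four 13-minute periods of each session. It is available at practice Levels 1 to 4 for the first 8 treatment hours and at Levels 1 and 2 for the next 8. Then: "During the final 4 hours of treatment, no visual feedback will be available".

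**The concern.** The form follows the calendar and ultrasound follows treatment hours. The two clocks run together in the Distributed schedule but not in the Sequenced one, where half of the therapy is delivered in the first week. A check that procedures remain safe is most useful while they are still being applied to the child, because something can then be changed for that child. If the first form comes after the last ultrasound session, this use of it is lost. The loss would fall in the cell where ultrasound is most concentrated in time. The form is also the only scheduled enquiry of child and parent about ultrasound effects that the protocol describes.

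**Working it through.** **Inputs.** Weekly hours come from the text of Treatment Design, Aim 1: Sequenced 10, 3, 3, 2, 2; Distributed 2 in each of 10 weeks. Ultrasound phases come from Aim 2: hours 1–8, hours 9–16, then none for hours 17–20. Assessment weeks come from the progress monitoring section: 5, 10 and 15. Cell size comes from Table 1: n=10.

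**Reproducing the plan's figure.** Sequenced: 10 + 3 + 3 + 2 + 2 = 20 hours. Distributed: 2 × 10 = 20 hours. Both match the stated dose. The SAP agrees that at 5 weeks the Intensive group has had 20 hours and the Distributed group 10.

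**Ceiling on ultrasound time.** Two 13-minute periods give 2 × 13 = 26 minutes per treatment hour at most, in hours 1–16 only.

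| Week | Sequenced: hours (cumulative) | Sequenced: ceiling, min | Distributed: hours (cumulative) | Distributed: ceiling, min |
|---|---|---|---|---|
| 1 | 10 (10) | 260 | 2 (2) | 52 |
| 2 | 3 (13) | 78 | 2 (4) | 52 |
| 3 | 3 (16) | 78 | 2 (6) | 52 |
| 4 | 2 (18) | 0 | 2 (8) | 52 |
| 5 | 2 (20) | 0 | 2 (10) | 52 |
| 6–8 | 0 (20) | 0 | 2 a week (16) | 52 a week |
| 9–10 | 0 (20) | 0 | 2 a week (20) | 0 |

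The total ceiling is the same in both schedules: 260 + 78 + 78 = 416 minutes, and 8 × 52 = 416 minutes. Only the spacing differs. In week 1 the ratio is 260 / 52 = 5.

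**Forms against exposure.**

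- Sequenced ultrasound cell: hour 16 is reached at the end of week 3. The forms come about 5 − 3 = 2, 10 − 3 = 7 and 15 − 3 = 12 weeks later. None of the three falls during exposure.
- Distributed ultrasound cell: hour 16 is reached at the end of week 8. The week-5 form falls within exposure, after 10 of 16 ultrasound hours. The other two come about 10 − 8 = 2 and 15 − 8 = 7 weeks after it. One of the three falls during exposure.

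The two-week gap assumes that the form is given at the end of week 5. If it were given early in that week the gap would be shorter, but weeks 4 and 5 are the final 4 hours without ultrasound, so it would still follow the last use.

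**Position of treatment hour 8.** Sequenced: at 2 hours a day, 8 / 2 = 4, so the fourth day of week 1. Distributed: 8 / 2 = 4, so the end of week 4. In both schedules 8 further hours with ultrasound available remain.

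**The case against.** The case for leaving the plan alone has several parts.

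*The form still does useful work.* Its purpose covers freedom from adverse effect as well as continuing safety. A form given two weeks after the last use can record effects that occurred, including late ones. Section 6.5 plans for about 15 children a year out of 40, so one child's answers can change practice for later children. This stands. A reader might infer that the form's purpose and timing flatly contradict each other, or that the form is useless in this cell. The documents support neither. What is lost is the check on a given Sequenced child during that child's own exposure.

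*Risk is low and other safeguards exist.* Section 12.1 rates ultrasound as no more than minimal risk and says that this imaging mode rarely warms the probe by even one degree. Section 12.2 limits each exposure to about 13 minutes, keeps it under half the session, and provides for probe cleaning and breaks. Section 6 has staff bring human-subjects issues to the principal investigator at once. A Sequenced child attends 5 + 3 + 3 = 11 visits in weeks 1 to 3, so there is ample contact. All this stands and lowers the weight of the point. None of it is a scheduled enquiry of child and parent during exposure. The section 12.2 limits are stated per period and per session, and do not mention two hours on one day.

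*The minutes are ceilings.* Use depends on the practice level reached, and hours 9 and 10 of Sequenced week 1 are already in the reduced phase. This is correct. The timing of the forms does not depend on it.

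*Comparing the two cells.* A reader might infer that different timing makes safety reports from the two ultrasound cells incomparable. The documents do not support that as a defect: neither plans a between-arm safety comparison, the SAP has no safety analysis, and the questionnaire's recall window is not given.

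*Ultrasound after hour 16.* Section 11.7.2 requires ultrasound video recording to track speech changes, so imaging outside treatment is conceivable. No assessment lists it, and section 11.1 makes image collection depend on the randomised condition.

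**Conclusion.** The point holds for one cell, Sequenced Distribution with ultrasound, planned n=10. The other 10 Sequenced children receive no ultrasound. In that cell 0 of 3 forms fall during exposure, against 1 of 3 in the Distributed ultrasound cell, and the first comes about two weeks after the last ultrasound use. The form cannot check that procedures remain safe for a Sequenced child while ultrasound is in use, including a first week with a ceiling of 260 minutes against 52.

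This is a modest monitoring gap with a cheap remedy. A reader might infer that children are being put at risk or that the trial's results are affected. The documents show no harm, and the timing of the form has no bearing on randomisation, the phrase-probe outcome or the mixed model.

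The conclusion assumes that children follow the planned schedule, that ultrasound is confined to treatment hours 1–16, and that the form is given only at the listed assessments.

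**What to change.** Reconcile the timing in the progress monitoring section with the Aim 1 schedule and the Aim 2 ultrasound phases. Add at least one Ultrasound Safety Form keyed to ultrasound exposure, at an existing treatment visit while ultrasound is still in use in both schedules. After treatment hour 8 would serve: that is week 1 in the Sequenced schedule and week 4 in the Distributed schedule. Keep the forms at weeks 5, 10 and 15, which still cover later effects. A form at hour 16 is optional; it marks the end of exposure and so does not supply the missing check. Give the added form outside the therapy hour so that treatment time is untouched.

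The cost is a sentence or two of protocol wording and one extra 5-minute form for about 20 children, or 20 × 5 = 100 minutes over the whole trial. It needs no extra visit or staff and no change to treatment or outcome timing. If the children have already been treated, report when each form was given relative to the last ultrasound session, and do not describe the Sequenced forms as monitoring during exposure.
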